5.4.1.1 Allowed OADs

As prior to randomisation:

- Metformin
- α -glucosidase-inhibitors
- DPP-4 inhibitors
- SGLT2 inhibitors
- Oral combination products (of the allowed individual OADs above)

5.4.1.2 OADs prohibited during trial treatment:

Below OADs must be discontinued upon randomisation visit (V2) and must not be initiated during the trial:

- Insulin secretagogues (SU and glinides)

5.5 Treatment after discontinuation of trial product

When discontinuing trial product(s), either at the scheduled EOT visit (V40) or if trial product is discontinued prematurely, the subject should be asked to attend the trial site for completion of the following visits:

- EOT visit (V40)

At this visit the subjects randomised to the two treatment arms should be switched to the following ‘washout’ insulin treatment and continue other oral antidiabetic treatment until the 7-day follow-up visit (V41):

- **IDegAsp arm:** Switch IDegAsp dose to BiAsp 30 BID. The total daily IDegAsp dose at end of the treatment period should be reduced by 20% and divided into two BiAsp 30 doses and administered with breakfast/lunch and evening meal.
- **IGlar + IAsp arm:** Switch IGlar dose to NPH insulin BID. The IGlar dose at the end of the treatment period should be reduced by 20% and divided into two NPH doses and administered in the morning and in the evening. IAsp doses should be continued as in the treatment period.

- 7-days follow-up visit (V41):

At this visit subjects should be switched to suitable marketed insulin product(s) at the discretion of the investigator.

- A 30-day follow-up visit (P42) – refer to section [8.1.9](#)

In addition, for subjects pre-term discontinued, monthly phone contacts (Px) as applicable, an abbreviated V28 (V28a), if applicable, and an additional abbreviated EOT visit (V40a) will be conducted as described in Sections [8.1.9](#) and [8.1.11](#) also refer to the flow chart (Section [2](#)).

5.6 Rationale for treatment

In patients not achieving treatment target on basal insulin, addition of either mealtime insulin or GLP-1 RA is recommended by the ADA/European Association for the Study of Diabetes (EASD) guidelines. The combination of basal insulin and mealtime insulin is the most commonly used; either as basal/bolus regimens or as combination products. Accordingly, this trial will provide information on the efficacy and safety of the combination product IDegAsp OD compared to IGlar OD + IA Sp OD and of the stepwise intensification of mealtime insulin with two different treatment intensification regimens.

Subjects treated with SU and glinides should discontinue the use of these at randomisation because the combination with trial insulin products could lead to an increased risk of hypoglycaemia.

Dosing is individual and the treat to target approach is used to optimise glycaemic control throughout the trial.

The subcutaneous administration form of all trial products is in accordance with approved documents as follows:

- IDegAsp: IB and/or EU SmPC and/or U.S. LI
- IGlar: U.S. LI/ EU SmPC
- IA Sp: EU SmPC and/or U.S. LI

IGlar has been chosen as the comparator as it is approved for OD use only, is commonly used for insulin initiation in T2DM subjects and is currently the most widely used basal insulin in many countries.

Based on data from the clinical development programme for IDegAsp, and the fact that there is no maximum dose of IDegAsp treatment, the chosen duration of the trial is considered appropriate for the purpose of obtaining meaningful information on efficacy and safety of IDegAsp when intensifying treatment from OD to BID.

The switch from trial insulin treatment to the ‘washout’ insulin (BiAsp 30 or NPH + IA Sp) between the EOT visit (V40) and the 7-day follow-up visit (V41), is done in order to provide basal insulin coverage while reducing the level of exogenous insulin present at antibody sampling and consequently to reduce the possibility for interference with antibody measurements.

6 Trial population

6.1 Number of subjects

Planned number of subjects to be screened meaning the number of subjects providing informed consent: 754.

Planned number of subjects to be randomised/started on trial products: 528.

Expected number of subjects to complete the trial: 449.

A screening failure rate of 30% and a premature discontinuation of trial drug/withdrawal rate of randomised subjects of 15% are expected.

6.2 Inclusion criteria

For an eligible subject, all inclusion criteria must be answered “yes”.

1. Informed consent obtained before any trial-related activities. Trial-related activities are any procedures that are carried out as part of the trial, including activities to determine suitability for the trial
2. Male or female, age \geq 18 years at the time of signing informed consent
Algeria: Male or female, age \geq 19 years at the time of signing informed consent
3. Diagnosed with type 2 diabetes mellitus
4. Treated with any basal insulin \geq 90 days prior to the day of screening
5. Subject not on any OAD(s) prior to trial participation OR subjects on stable daily dose(s) of OAD(s) for at least 90 days prior to screening visit (V1). The OAD(s) include any of the following anti-diabetic drug(s)/regimen:
 - a. Biguanides (metformin \geq 1500 mg or maximum tolerated dose documented in the subject medical record)
 - b. Other OADs (\geq half of the maximum approved dose according to local label or maximum tolerated dose as documented in subject medical record):
 - i. Insulin secretagogues (SU and glinides)
 - ii. DPP-4 inhibitors
 - iii. α -glucosidase inhibitors
 - iv. SGLT-2 inhibitors
 - v. Oral combination products (of the allowed individual OADs)
6. HbA_{1c} 7.0-10.0% (53-86 mmol/mol) (both inclusive) by central laboratory analysis
7. Body mass index (BMI) \leq 45.0 kg/m²

8. Ability and willingness to adhere to the protocol including self-measurement of plasma glucose according to the protocol

6.3 Exclusion criteria

For an eligible subject, all exclusion criteria must be answered “no”

1. Known or suspected hypersensitivity to trial product(s) or related products
2. Previous participation in this trial. Participation is defined as signed informed consent
3. Female who is pregnant, breast-feeding or intends to become pregnant or is of child-bearing potential and not using adequate contraceptive methods (adequate contraceptive measures as required by local regulation or practice)
4. Participation in any clinical trial of an approved or non-approved investigational medicinal product within four weeks prior to the day of screening (V1)
5. Any chronic disorder or severe disease which, in the opinion of the investigator, might jeopardise subject’s safety or compliance with the protocol
6. Acute decompensation of glycaemic control requiring immediate intensification of treatment to prevent severe metabolic dysregulation (e.g. diabetes ketoacidosis) \leq 90 days prior to the day of the screening
7. Any of the following: myocardial infarction, stroke or hospitalization for unstable angina or transient ischaemic attack within the past 180 days prior to the day of screening and between screening and randomisation
8. Subjects presently classified as being in New York Heart Association (NYHA) Class IV
9. Planned coronary, carotid or peripheral artery revascularisation known on the day of screening
10. Renal impairment measured as estimated Glomerular Filtration Rate (eGFR) value of < 60 ml/min/1.73 m² as defined by KDIGO 2012 classification using isotope dilution mass spectrometry (IDMS) for serum creatinine measured at screening
11. Impaired liver function, defined as ALT \geq 2.5 times upper normal limit (UNL) at screening
12. Inadequately treated blood pressure defined as Grade 3 hypertension or higher (Systolic \geq 180 mmHg or diastolic \geq 110 mmHg) at screening
13. Treatment with any medication for the indication of diabetes or obesity other than stated in the inclusion criteria in a period of 90 days before the day of screening
14. Anticipated initiation or change in concomitant medications (for more than 14 consecutive days) known to affect weight or glucose metabolism (e.g. treatment with orlistat, thyroid hormones, or corticosteroids)
15. Proliferative retinopathy or maculopathy requiring acute treatment. Verified by fundus photography or dilated fundoscopy performed within 90 days prior to randomisation

16. Presence or history of malignant neoplasms within the past five years prior to the day of screening. Basal and squamous cell skin cancer and any carcinoma in-situ are allowed

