- Informed consent obtained before any trial-related activities. Trial-related activities are any procedures that are carried out as part of the trial, including activities to determine suitability for the trial
- Male or female, age \geq 18 years at the time of signing informed consent
Algeria: Male or female, age \geq 19 years at the time of signing informed consent
- Diagnosed with type 2 diabetes mellitus
- Treated with any basal insulin \geq 90 days prior to the day of screening
- Subject not on any OAD(s) prior to trial participation OR subjects on stable daily dose(s) of OAD(s) for at least 90 days prior to screening visit (V1). The OAD(s) include any of the following anti-diabetic drug(s)/regimen:
 - a. Biguanides (metformin \geq 1500 mg or maximum tolerated dose documented in the subject medical record)
 - b. Other OADs (\geq half of the maximum approved dose according to local label or maximum tolerated dose as documented in subject medical record):
 - i. Insulin secretagogues (SU and glinides)
 - ii. Di-peptidyl-peptidase IV (DPP-4) inhibitors
 - iii. α -glucosidase inhibitors
 - iv. Sodium/glucose co-transporter 2 (SGLT-2) inhibitors
 - v. Oral combination products (of the allowed individual OADs above)
- HbA_{1c} 7.0-10.0% (53-86 mmol/mol) (both inclusive) by central laboratory analysis
- Body mass index (BMI) \leq 45.0 kg/m²

Key exclusion criteria:

- Participation in any clinical trial of an approved or non-approved investigational medicinal product within four weeks prior to the day of screening (V1)
- Any chronic disorder or severe disease which, in the opinion of the investigator, might jeopardise subject's safety or compliance with the protocol
- Acute decompensation of glycaemic control requiring immediate intensification of treatment to prevent severe metabolic dysregulation (e.g. diabetes ketoacidosis) \leq 90 days prior to the day of the screening and between screening and randomisation
- Any of the following: myocardial infarction, stroke or hospitalization for unstable angina or transient ischaemic attack within the past 180 days prior to the day of screening and between screening and randomisation
- Renal impairment measured as estimated Glomerular Filtration Rate (eGFR) value of < 60 ml/min/1.73 m² as defined by KDIGO 2012 classification using isotope dilution mass spectrometry (IDMS) for serum creatinine measured at screening

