5.3 Treatment of subjects

Subjects with T2DM treated with any basal insulin with or without OAD(s) can enter the trial if they have an HbA_{1c} between 7.0-10.0% (both inclusive).

Subjects will attend a screening visit (V1) where inclusion and exclusion criteria will be assessed.

If eligible, subjects will be randomised to their trial insulin treatment at the randomisation visit (V2), refer to Sections [5.3.1](#) and [5.3.2](#).

At randomisation subjects must discontinue pre-trial insulin, SU and glinides. Treatment with other OADs should continue during the trial as described in Section [5.4](#).

For subjects in both treatment arms diet and exercise counselling should be continued as per the standard of care at the investigational site.

At the EOT visit (V40) subjects should be switched to ‘washout’ insulin as described in Section [5.5](#)

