6.4 Randomisation criteria

Not applicable for this trial.

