8.1.7 Randomisation visit (V2)

Randomisation (V2) should take place within 14 days after the screening visit (V1). All results from screening assessments, including laboratory results, ECG and eye examination must be available, reviewed, dated and signed by the investigator and the in/exclusion criteria carefully reviewed to ensure subject eligibility prior to randomisation.

Randomisation of subjects will be done using IWRS, see Sections [10](#) and [11](#).

At V2 trial insulin products will be supplied to the subject after having completed the IWRS dispense call, see Section [10](#). Investigator or delegate staff will ensure proper training in trial product and pen handling. For subjects in the IGlar arm, the training must include pen differentiation. Directions for use (DFUs) will be provided to the subjects, refer to Section [8.6.3](#).

Hand-out of the DFU(s) to the subject must be documented in the subject's medical file.

At randomisation subjects must discontinue their pre-trial insulin, SU and glinides and the stop-date(s) must be recorded in the subjects' medical notes and transcribed into the eCRF. Treatment with other OADs should continue unchanged during the trial, see Section [5.4](#).

PRO questionnaires including baseline hypoglycaemia questionnaire (BHQ) must be completed by the subjects - please refer to Section [8.6.1](#).

For further details on trial procedures and assessments, refer to the Flow chart (Section [2](#)).

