3.1 Initiation of IGlar

Subjects receiving OD basal insulin will transfer unit-to-unit to IGlar OD. Subjects receiving more than OD basal insulin should reduce the initial total daily dose by 20% or according to local labelling and transfer to IGlar OD.

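### Exclusion criterion 6 in protocol section 6.3 stops at screening, but the protocol summary also excludes acute decompensation between screening and randomisation

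*Protocol*

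**What the plan says.** The protocol states the acute decompensation exclusion twice, with different time windows.

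- **Section 6.3, criterion 6:** the window is "severe metabolic dysregulation (e.g. diabetes ketoacidosis) \leq 90 days prior to the day of the screening". The text ends there and criterion 7 follows.
- **Section 1, key exclusion criteria:** the window is "90 days prior to the day of the screening and between screening and randomisation".

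The neighbouring cardiovascular exclusion, criterion 7, reads "within the past 180 days prior to the day of screening and between screening and randomisation" in section 6.3, and the summary gives it the same reach.

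On the interval itself, section 8.1.7 says "Randomisation (V2) should take place within 14 days after the screening visit (V1"). Section 6.4, where separate randomisation criteria would stand, says only "Not applicable for this trial". Global amendment no. 1 changes section 1 only in the mmol/mol range for HbA1c and has no item for section 6.3.

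**The concern.** Section 6.3 is the list a site works from. It requires every exclusion criterion to be answered no, and section 8.2.5 cites a criterion by its 6.3 number. A site following it would correctly answer no to criterion 6 for a subject who had ketoacidosis after V1, although the summary excludes that subject.

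The interval comes just before a change of regimen. Section 5.3 says "At randomisation subjects must discontinue pre-trial insulin, SU and glinides". In the IGlar arm, Appendix A section 3.1 adds a cut in basal dose for some subjects: "Subjects receiving more than OD basal insulin should reduce the initial total daily dose by 20% or according to local labelling". A subject who has just needed immediate intensification should not be kept out of that switch by discretion alone.

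The mismatch also reaches the analysis. Section 6.6 item 1 requires trial product to be stopped when a subject was included against the criteria, and the per-protocol definition (protocol 17.3, SAP 2.3) removes anyone who met an exclusion criterion. Both depend on which text is followed.

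**Working it through.** The plan gives no figure for this point. The check is a comparison of texts, followed by a bound on the size.

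**1. The two criteria side by side**

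| Criterion | Section 1 summary | Section 6.3 |
|---|---|---|
| Acute decompensation (6) | 90 days before screening, plus screening to randomisation | 90 days before screening only |
| Cardiovascular events (7) | 180 days before screening, plus screening to randomisation | Same as summary |

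The summary is the longer version of criterion 6, so abbreviation does not explain the difference.

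**2. Does another rule close the gap?**

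- Section 6.4 sets no randomisation criteria.
- The eligibility review before randomisation (8.1.7) applies criterion 6 as it is written.
- Inclusion criteria 4 and 5 and exclusion criterion 13 look back from screening. The qualifying HbA1c is the V1 result (8.5.2.1).
- The rescue limits in 6.5 start at baseline.
- Criterion 5 ("Any chronic disorder or severe disease which, in the opinion of the investigator, might jeopardise" the subject's safety or compliance) has no look-back limit and could be used, but it is a matter of opinion. The summary makes the exclusion mandatory.

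None of these firmly replaces the missing clause.

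**3. Size of the window**

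Inputs: 90 days (6.3), 14 days (8.1.7), 528 randomised subjects (6.1).

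- Uncovered share of the summary's window: 14 / (90 + 14) = 0.135, about 13%.
- Maximum exposure: 528 × 14 = 7392 person-days; 7392 / 365.25 = 20.2 person-years.
- Expected subjects at an assumed 1 event per 100 person-years: 20.2 × 0.01 = 0.2.
- Expected subjects at an assumed 10 events per 100 person-years: 20.2 × 0.10 = 2.0.

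**4. One subject under the two readings**

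Take a subject who decompensates between V1 and V2 and is randomised to IDegAsp.

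- Under criterion 6 in section 6.3, the subject is not in violation of it, stays on trial product and can be in the per-protocol set.
- Under the summary, the subject was included in violation, must stop trial product and leaves the per-protocol set. Stopping before week 26 also adds the 0.4% penalty to the week 26 HbA1c (protocol 17.4, SAP 2.4).

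One extra penalised subject among 264 moves the arm mean by 0.4 / 264 = 0.0015 percentage points, against a margin of 0.4.

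**5. Insulin at the switch**

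Let D be the previous total daily basal dose.

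- IGlar arm, previously more than once daily, default 20% cut: basal 0.8D, plus 4 U of IAsp (Appendix A 3.3). The total 0.8D + 4 is below D only when D exceeds 20 U.
- IDegAsp arm: unit-to-unit transfer (Appendix A 3.2) to a product that is 70% basal (3.1.3). The total stays at D and the basal part becomes 0.7D.

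**The case against.** The mismatch itself is not in dispute. The case against giving it weight has four parts.

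**Direction.** No text ranks section 6.3 above section 1. Within 6.3 only criterion 7 carries the clause; criteria 4, 6, 9, 13 and 16 are anchored to screening. The documents do not prove which text is the slip. This stands as far as it goes: choosing the longer window is a safety judgement, supported by criterion 7.

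**Other cover.** Criterion 14, on anticipated changes in medication affecting glucose metabolism for more than 14 consecutive days, might catch a lasting new drug. Its listed examples are not antidiabetics, however, and a short increase in basal dose that ends at V2 would escape it. A ketoacidosis admission after consent would be a reportable serious adverse event, so the site would know of it at the V2 review. After randomisation there are weekly contacts, rescue limits and discontinuation for safety. These lower the risk, but they are discretionary, arguable or act too late.

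**Dosing.** The 20% cut applies to some subjects in one arm, total insulin need not fall, and doses are titrated weekly by up to 8 U. This stands. Withdrawal of SU and glinides is the stronger part of the argument, and it concerns only users of those drugs.

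**Size and cost.** The event rate has no basis in the documents, and 20.2 person-years assumes that every subject uses all 14 days. An amendment also needs ethics approval and regulatory submission. Both points are fair, and they limit the priority of the change.

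**Conclusion.** The concern holds. Two current parts of the protocol give different windows for the same safety exclusion, and no other rule firmly covers the interval that section 6.3 leaves open.

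The consequence is minor. The estimate of about 0.2 to 2 subjects rests on the assumed event rates and on full use of the 14 days, before any other exclusion acts. The sample size is unaffected, and the effect on the primary full-analysis-set result is negligible. What changes is who may be randomised and, for the few subjects concerned, who must stop trial product and who belongs in the per-protocol set. It is worth correcting, at low priority.

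**What to change.** Extend criterion 6 in section 6.3 to the day of randomisation, using the closing clause that criterion 7 already has. Leave the summary as it is. The V2 eligibility check, section 6.6 item 1 and the per-protocol definition refer to the criteria generically, so they need no further edits.

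The cost is one clause and, at the assumed rates, about 0 to 2 further exclusions. Amendments need ethics approval before implementation and regulatory submission (section 25), and the clause has effect only while subjects are still being randomised, so it is best included with another amendment.

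If recruitment has already closed, record before database lock which wording governs per-protocol membership. Protocol 17.3 and SAP 2.3 already require exclusions to be documented by then.

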6.4 Randomisation criteria

Not applicable for this trial.

6.5 Rescue criteria

If any of the fasting SMPG values taken on three consecutive days or if any of the FPG samples analysed by the central laboratory exceed the limit of:

- 15.0 mmol/L (270 mg/dL) from baseline to end of week 12
- 13.3 mmol/L (240 mg/dL) from week 13 to end of week 38

and if no treatable inter current cause for the hyperglycaemia has been identified, the subject must be called for a confirmatory FPG measurement at a scheduled or unscheduled visit as soon as possible. A confirmatory FPG must be obtained and analysed by the central laboratory. If this FPG exceeds the limits described above, the trial product must be discontinued.

The subject should be prescribed alternative therapy at investigator's discretion, and be retained in the trial.

If prematurely withdrawn from trial drug, effort should be made to follow the procedures described in Section [8.1.11](#). Also refer to Section [5.5](#).

6.6 Criteria for premature discontinuation of trial product

Efforts must be made so that subjects attend and complete all scheduled visit procedures. Subjects should stay in the trial irrespective of lack of adherence to randomised treatment, lack of adherence to visit schedule or missing assessments. Only subjects who decline any further contact with the site in relation to the trial will be considered as withdrawn from the trial (see Section [6.7](#)).

The subject may be prematurely discontinued from trial product at the discretion of the investigator due to a safety concern or if judged non-compliant with trial procedures.

The subject must be prematurely discontinued from trial product if the following applies:

1. Included in the trial in violation of any of the inclusion and/or exclusion criteria
2. Pregnancy
3. Intention of becoming pregnant
4. Initiation or significant change in concomitant medications for more than 14 calendar days which in the investigator's opinion could affect weight or glucose metabolism
5. Simultaneous participation in another clinical trial of an approved or non-approved investigational medicinal product
6. The fasting SMPGs values taken on three consecutive days or any FPG samples analysed by the central laboratory exceeding the limit of (refer to section [6.5](#)):
 - 15.0 mmol/L (270 mg/dL) from baseline to end of week 12
 - 13.3 mmol/L (240 mg/dL) from week 13 to end of week 38

Subjects discontinued from trial product should be prescribed alternative therapy at investigator's discretion, and be retained in the trial.

For procedures to be performed for subjects discontinuing trial product prematurely, see Sections [8.1.11](#) and [5.5](#).

